9. STUDY ENROLLMENT AND WITHDRAWAL

Introduction

Potential subjects will be males and females, all ethnicities, 22-65 years of age, living within or near the Louisville metropolitan area, with carnosine levels below the median value of the population.

Criteria to Invite for Screening Visit (Visit # 1)

To be considered eligible to participate in the screening visit of the study, the participant must meet the following criteria:

1. Living within 30 miles radius of Louisville Metropolitan area (Kentucky counties: Jefferson, Bullitt, Spencer, Shelby, and Oldham; Indiana counties: Clark, Floyd).
2. Age 22-65 at time of baseline assessment (Visit # 2)
3. Healthy subjects
4. Subjects with a diagnosis that puts them at high risk for acute or chronic disease, specifically but not limited to hypertension or diabetes, are eligible for the study if the condition is treated by a physician or provider and is controlled via medications and or lifestyle that are otherwise not excluded by the exclusion criteria.
5. Consumes some type of meat/fish at least once a month during the past 3 months

6. Agree to complete all four study visits (one screening, one baseline, two follow-up visits)
7. Will be living in the Louisville Metropolitan area throughout the study period (May through September), with planned vacations of no more than 2 weeks away from study area.
8. Agree to take supplement/placebo intervention during the study period and follow study intervention regimen

Main Study Inclusion Criteria (Visits # 2-4)

[figure not shown]
To be considered eligible to participate in this study, the participant must meet the following criteria:

1. Living within 30 miles radius of Louisville Metropolitan area (Kentucky counties: Jefferson, Bullitt, Spencer, Shelby, and Oldham; Indiana counties: Clark, Floyd).
2. Age 22-65 at time of baseline assessment (Visit # 2)
3. Consumes some type of meat/fish at least once a month during the past 3 months
4. Carnosine level less than median (value of the population)
5. Agree to complete all four study visits (one screening, one baseline, two follow-up visits)
6. Will be living in the Louisville Metropolitan area throughout the study period (May through September), with planned vacations of no more than 2 weeks away from study area.
7. Agree to take supplement/placebo intervention during the study period and follow study intervention regimen

Exclusion Criteria (All Visits)

Participants will be excluded from the study if they have any of the following conditions:

1. Consumed any carnosine supplement of more than 6 grams per a week in the past 4 weeks (one month)
2. Current / ongoing treatment for substance abuse
3. Currently undergoing treatment or have conditions which may cause participant to be immunosuppressed
4. Diseases Affecting Peripheral Cell Count (i.e. Autoimmune Diseases – Hashimoto, Rheumatoid Arthritis, SLE, Rheumatoid Arthritis, Sjogren syndrome, Ankylosing Spondylitis, Takayasu arteritis, Kawasaki disease, Polyarteritis nodosa.)
5. Diseases Affecting Bone Marrow capacity
6. Diagnosis of any active cancer
7. Recent organ / kidney transplant or replacement (Active/Long-Term Medications)
8. Type 1 Diabetes Mellitus
9. Untreated thyroid disease
10. Untreated anemia
11. Current acute infections (Influenza, fever, etc.)
12. HIV positive status
13. Active/current Hepatitis HepA, HepB or HepC or in past 6 months
14. Pregnant / lactating or planning to

15. Prisoners / vulnerable populations
16. Other medical conditions that compromise completion of study
17. Unwilling to provide consent

Special Conditions of Exclusion (Screening or Main Study)

Candidates with the following conditions or history may be excluded:

1. **Local reactions:** diarrhea, stomach upset, tingling sensation in extremities, rash or itchiness, dry mouth, changes in appetite, feelings of tiredness, or vivid dreams.
2. **Systemic reactions:** fever, allergic reaction, anaphylaxis or any clinical untoward event that occurred with a known cause of taking dietary supplement.
3. **Abnormal laboratory results** which are deemed clinically significant with a known cause of taking dietary supplement.
4. **Pregnancy and breast-feeding:** Currently, there is not enough reliable information about the safety of taking carnosine supplement during pregnancy or breast-feeding. Hence, participants/candidates who are currently pregnant or breast-feeding or plan to be pregnant/breast-feeding during the study period will not be enrolled in the study.
5. **Low blood pressure:** Carnosine synthesized in the body has been found to decrease blood pressure via influencing the autonomic nervous system.⁴³ Hence, in theory, taking supplemental carnosine might lower blood pressure and or exacerbate lowering of blood pressure in people taking antihypertensive medications. Hence, all participants taking blood pressure lowering medication will be cautioned for this interaction and advised that in case of an episode of low blood pressure to discontinue study supplement and immediately seek medical attention from a licensed healthcare provider.
6. **Low blood sugar:** Carnosine synthesized in the body has been found to decrease blood sugar via influencing the autonomic nervous system.⁴³ Hence, in theory, taking supplemental carnosine might lower blood sugar and or exacerbate lowering of blood sugar in people taking blood sugar lowering medications. Hence, all participants taking blood sugar lowering medication will be cautioned for this interaction and advised that in case of an episode of low blood sugar to discontinue study supplement and immediately seek medical attention from a licensed healthcare provider.

Prescreening (Prior to Consent)

Prescreening participants includes reviewing personal or protected health information for inclusion/exclusions prior to consent. Also, currently we have a database of about 1,000 subjects who have previously participated or contacted us for participating in one of our research studies and expressed interest in participating in future research studies. Only candidates who have given permission to contact them for future studies will be prescreened for relevant eligibility criteria and contact information. The script for phone and email/letter communication is detailed in Appendix C.

Consent

All participants enrolled in this clinical trial will be identified as males or females, age 22-65, living within 30 miles radius of Louisville metropolitan area, and with carnosine levels less than the median of local population. After being identified (from existing database, from clinics, flyers, or other routes), potential participants will be approached by one of the investigators or research coordinators. The information provided to the potential participant is included in the informed consent. The informed consent will provide information regarding PM_{2.5} pollution, prevalence of PM_{2.5} pollution in the study area, synthesis and natural role of carnosine in the body, natural and supplemental sources of carnosine, cornstarch (constituent of placebo), and will include information regarding possible risks of participation.

Randomization

Eligible participants identified from Screening (Visit # 1) will be randomized in to supplement or placebo groups by 1:1 distribution. Randomization will be performed in accordance with written standard operating procedures by personnel that are not involved in the selection, screening, or enrollment of subjects and blinded as to study documentation. Randomization to supplement assignment will be conducted using a web access database created and maintained by the Randomization Unit. After the investigator or research coordinator verifies that screening testing is complete and the inclusion and exclusion criteria for the study have been satisfied, an un-blinded member of the Randomization Unit will have secured access to the participant's supplement assignment. The participant will be randomized a minimum of 2 days before the scheduled date of the baseline assessment (Visit # 2) to arrange for the timely availability of the study supplement. See Manual of Operations for details

Stopping Early or Withdrawal from the Study

Monitoring rules and statistical boundaries for adverse outcomes are further detailed in Section 15 "Data and Safety Monitoring Board". Below is the outline for recusal or withdrawal of participant from the study due to a non-health / safety related reason.

[figure not shown]
Participants that have consumed study supplement for at least 4 weeks during the duration of the study period, but missed taking the study supplement for no more than 1 week during the study period will still be followed if feasible, and included in intent to treat analysis.

Participants that withdraw from the study before Follow-Up # 1 (Visit # 3) or do not complete Visit # 3 will be considered lost to follow-up. Existing data of these participants will be retained for further analysis.

Screen Failure

Candidates are considered screen failures when they meet one of the following criteria after signing consent:

1. Screening (Visit # 1) data reveals that the candidate is ineligible
OR

2. Candidate withdraws and does not complete Baseline Assessment (Visit # 2)

Discontinued

Participants are considered discontinued when they meet one or more of the following criteria:

1. Participant withdraws consent after being randomized
OR
2. Participant withdraws consent after completion of Baseline Assessment (Visit # 2)
OR
3. Participant fails to follow study supplement regimen
OR
4. Participant is unable to fulfill the inclusion/exclusion criteria during the study
OR
5. Participant refuses/is unable to provide critical data at follow-up visits as deemed necessary by the investigator
OR
6. Participant is withdrawn after randomization by investigator for reasons that may compromise completion of the study

Medical or Health Concerns

Participants will be instructed that in an event of an acute health concern (related or unrelated to the study supplement), they should immediately discontinue the study supplement and seek medical attention from a licensed healthcare provider. Participants will be provided with a study identification card. This card will contain the following information: name of the study, name of study institution, a statement to the effect of *“each capsule may contain 0.5 grams of L-Carnosine or 0.5 grams of cornstarch”*, method of contacting the study physician, and a method of contacting the study coordinator.

Participants may be able to re-start supplement regimen and continue the randomization after detailed discussions with the study physician. The study physician may seek advisement from the DSMB on these matters.

Compensation

Participants will be given a University of Louisville branded prepaid VISA gift card for participating in the study. The following information will be collected: full name, address, and social security number. Social security number will not be saved. As required by the Internal Revenue Service, participants may need to report the payment as income on their taxes. If participants choose not to provide their social security number or other required information, they will not be paid for participating in the study. Participants can still participate in the study even if they don't want to be paid.

Participants will be compensated for completing a clinical visit as per the following schedule:

Visit Description	Amount
Screening (Visit # 1)	\$25
Baseline Assessment (Visit # 2)	\$50
Follow-Up # 1 (Visit # 3)	\$75
Follow-Up # 2 (Visit # 4)	\$100
4-12 Month Safety Check (Visit # 5)*	None

*Visit # 5 is not an actual physical visit, contact will be made via phone, email, or mailed paper survey

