Follow-Up # 1 will occur ~6 weeks after initiation of study supplement at the baseline assessment (Visit # 2) (Figure 5). Participants attending follow-up # 1 (Visit # 3) will have already been taking the study supplement for at least 5 weeks and no more than 7 weeks (6 weeks \pm 1 from Visit # 2). The following activities will be carried out at Follow-Up # 1:

1. Update Demographics and Contact Information
2. Update Questionnaire data on Medical History, Medications, and Women's Health
3. Questionnaire data Exposure to Environmental Pollution, Sleep, Diet, Exercise, Tobacco
4. Blood sample collection (~3 tablespoons or ~45ml)
5. Urine sample collection (~2 tablespoons or ~30ml)
6. Arterial stiffness test (SphygmoCor)
7. Physical strength test (hand grip test, step test, calf raise test)
8. Review the participant's dietary supplement regimen and any instances of deviation in regimen (missed or over consumption).
9. Provide 4 more weeks of study dietary supplement capsules (carnosine or placebo)
10. Discuss any side-effects which may have occurred or may arise from study supplement. Discuss any health changes during the study period.
11. Prepaid \$75 VISA gift card

Participants may be excluded from the study if any of the above data collection is not completed or meets an exclusion criterion during this period.

Follow-Up # 2 (Visit # 4)

Follow-Up # 2 will occur ~12 weeks after initiation of study supplement at the baseline assessment (Visit # 2) (Figure 6). Participants attending follow-up # 2 (Visit # 4) will have already been taking the study supplement for at least 10 weeks and no more than 12 weeks (11 weeks \pm 1 from Visit # 2). The following activities will be carried out at Follow-Up # 2:

1. Update Demographics and Contact Information

2. Update Questionnaire data on Medical History, Medications, and Women's Health
3. Questionnaire data Exposure to Environmental Pollution, Sleep, Diet, Exercise, Tobacco
4. Blood sample collection (~3 tablespoons or ~45ml)
5. Urine sample collection (~2 tablespoons or ~30ml)
6. Arterial stiffness test (SphygmoCor)
7. Physical strength test (hand grip test, step test, calf raise test)
8. Review the participant's dietary supplement regimen and any instances of deviation in regimen (missed or over consumption).
9. Discuss any side-effects which may have occurred or may arise from study supplement.
Discuss any health changes during the study period.
10. Prepaid \$100 VISA gift card

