Participants may be excluded from the study if any of the above data collection is not completed or meets an exclusion criterion during this period.

4 – 12 Month Safety Check (Visit # 5)

Although this interaction is termed as a “Visit”, it will not involve participants to physically be present. A follow-up email / phone call / mailed paper questionnaire will be conducted 4-12 months after the end of supplement intervention (Figure 7). This contact will focus on updating about any SAEs & medical / medication history changes since end of intervention:

1. Update Demographics and Contact Information
2. Questionnaire data on Medical / Medications History since end of intervention
3. Questionnaire data on adverse effects or SAEs since end of intervention.
4. No monetary compensation for this follow-up / check.

Participants will not be excluded from the study if any of the above data collection is not completed. Instead, they will be categorized as “lost to safety follow-up”.

Safety Evaluations during Study Visits

Adverse events will be assessed during Visit # 3 and Visit # 4 and through the 12 months after participants have stopped taking study supplement. The following will be documented in the adverse event reporting system:

1. **Local reactions:** diarrhea, stomach upset, tingling sensation in extremities, rash or itchiness, dry mouth, changes in appetite, feelings of tiredness, or vivid dreams.
2. **Systemic reactions:** fever, allergic reaction, anaphylaxis or any clinical untoward event that occurs within 30 days of beginning study supplement.
3. **Abnormal laboratory results** which are deemed clinically significant.
4. **Pregnancy and breast-feeding:** Currently, there is not enough reliable information about the safety of taking carnosine supplement during pregnancy or breast-feeding. Hence, participants/candidates who are currently pregnant or breast-feeding or plan to be pregnant/breast-feeding during the study period will be “discontinued” from the study.

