16. TRIAL MANAGEMENT

Institutional Review Board (IRB) AND Informed Consent

This protocol and the informed consent document and any subsequent modifications will be reviewed and approved by the IRB or ethics committee responsible for oversight of the study. A signed consent form will be obtained from the participant. The consent form will describe the purpose of the study, the procedures to be followed, and the risks and benefits of participation. A copy of the consent form will be given to the subject and this fact will be documented in the participant's medical record if recruited from a clinic.

Informed Consent Process

Potential participants will be approached by one of the study investigators or research coordinators. Information regarding study participation will be provided to the potential participant. The informed consent includes descriptions of all study related procedures, all possible risks to participant, and the time commitment involved with participating. All consent forms will have IRB approval. Individuals who agree to participate will receive a copy of the signed informed consent. The research staff member obtaining consent will document the informed process in the participant's chart if recruited from a clinic.

Risks Associated with Manufacturing and Consuming of Dietary Supplement

Manufacturing Dietary Supplement

Supplement manufacturing is done under strict sterile conditions; however, there is a rare chance that the capsules could become contaminated while being processed. Quality control checks will be done on the manufacturing process, and if the tests reveal break in protocol or contamination, the participant will be notified and instructed on whether or not he/she should be treated with antibiotics. The participant will be diligently assessed for adverse reactions or events at each follow-up visit (Visit # 3 and Visit # 4). If the participant notes a fever, he/she will be requested to notify the investigator/study team immediately.

Consuming Dietary Supplement

Possible risks of Carnosine supplementation include: tingling of upper / lower extremities, drop in blood pressure, nausea, vomiting, stomach upset.

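### Section 9 lets a local reaction, with no limit on cause or timing, count as grounds for exclusion and does not confine this to before randomisation, so a randomised participant could be removed for a supplement side effect

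*Combined protocol and SAP*

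**What the plan says.** Section 9 contains a list headed "Special Conditions of Exclusion (Screening or Main Study". Its lead-in reads "Candidates with the following conditions or history may be excluded". Item 1, local reactions, is: "diarrhea, stomach upset, tingling sensation in extremities, rash or itchiness, dry mouth, changes in appetite, feelings of tiredness, or vivid dreams". It carries no condition on cause, timing or severity. Item 2, systemic reactions, ends with "any clinical untoward event that occurred with a known cause of taking dietary supplement", and item 3, laboratory results, is limited to those "which are deemed clinically significant with a known cause of taking dietary supplement".

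Section 10, Safety Evaluations during Study Visits, opens its list with "The following will be documented in the adverse event reporting system" and gives the same local reactions, word for word, as its item 1. Section 16, under Consuming Dietary Supplement, states: "Possible risks of Carnosine supplementation include: tingling of upper / lower extremities, drop in blood pressure, nausea, vomiting, stomach upset".

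The Visit 3 and Visit 4 descriptions in Section 10 each close by saying that a participant may be excluded if data collection is incomplete or the participant "meets an exclusion criterion during this period". In Section 9, the fourth criterion under Discontinued is being unable to fulfil the eligibility criteria during the study.

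**The concern.** The same symptoms appear as a reason to exclude and as an outcome to count. If the exclusion can operate after the first capsule, a participant who develops tingling or stomach upset on carnosine may be taken out of the study because of it. Where the supplement causes the reaction, removal depends on treatment and falls more heavily on one arm. Those who remain on carnosine are then a group selected for tolerance, and the randomised comparison of EPCs at 12 weeks is no longer between the groups that were randomised.

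The exclusion is also left to judgement, with nothing in item 1 to say how severe or how clearly supplement-related a reaction must be. Two coordinators could treat the same complaint differently. At entry, item 1 read literally also covers ordinary tiredness or dry mouth unrelated to any supplement.

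**Working it through.** The plan states no figure on this point, so the check is a comparison of its own passages.

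1. **Scope of the list.** The heading covers screening and the main study. Section 9 heads its main-study inclusion criteria with Visits 2 to 4, and its general exclusion criteria with all visits. Visits 3 and 4 take place on supplement, after randomisation.

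2. **Limits within the list.** Items 2 and 3 are tied to a known supplement cause. Item 1 is not, and it has no time limit.

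3. **Overlap with safety.** All eight local reactions are also on the Section 10 recording list. Two of them, tingling and stomach upset, are named in Section 16 as possible risks of carnosine. Tiredness is on the recording list but is not among the Section 16 risks.

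4. **Route from reaction to removal.** Three pieces of text re-apply eligibility after randomisation: the closing sentence for Visit 3, the same sentence for Visit 4, and the fourth discontinuation criterion in Section 9. None says which exclusion list it means, and none exempts the Special Conditions.

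5. **What removal would cost.** At Visit 3 the blood draw is item 4 and the side-effect discussion item 10, so the 6-week sample need not be lost. The Visit 4 endpoint would be. Section 9 mentions intent-to-treat only for people with at least 4 weeks of supplement and no more than 1 week missed. Section 15 says people without the required observations will be listed and evaluated separately as necessary. No passage keeps a participant excluded for a reaction in the efficacy analysis.

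6. **Whether the events survive.** Section 10 requires the reactions to be documented and assesses adverse events through 12 months after supplement stops. Section 13 requires causally related events to be followed until they resolve or stabilise. The Section 14 holding threshold for gastrointestinal events uses total enrolment. One gap remains: Section 13 keeps Grade 1 events out of the electronic case report form, so a mild reaction could support an exclusion without appearing there.

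7. **Size, by assumption only.** The documents give no reaction rate. Suppose reactions occur in 10% to 20% on carnosine and 5% on placebo, every reactor is removed, and those removed differ from those retained by d = 0.3 to 0.5 SD in EPC response.
   - Removals out of 200 per arm: 200 × 0.10 = 20 to 200 × 0.20 = 40 on carnosine, against 200 × 0.05 = 10 on placebo.
   - Shift in the arm difference = d × (carnosine rate − placebo rate): 0.3 × (0.10 − 0.05) = 0.015 SD to 0.5 × (0.20 − 0.05) = 0.075 SD.
   - For scale, Section 8 plans on a detectable effect of 0.5 SD; 0.075 / 0.5 = 15% of that.
   - With equal rates in the arms, or nobody removed, the shift is zero.

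**The case against.** The best case against is that the list is an entry screen by history. The lead-in speaks of candidates, and Section 9 uses that word for screen failures but participants for discontinuation. Neighbouring items were rewritten between the two lists: systemic reactions are tied to a past supplement cause in Section 9 but to the first 30 days of study supplement in Section 10, and pregnancy bars enrolment in one but leads to discontinuation in the other. That looks like an entry version and an on-study version. Reactions on supplement also have their own route: review by the study physician and the monitoring board (Section 10), possible restart (Section 9) and halting of delivery (Section 14).

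This makes the entry-only reading plausible, perhaps the intended one. It does not make it the only one. The documents do not keep the two words apart: the pregnancy item in both lists says participants/candidates. Items 5 and 6 of the Section 9 list address people already taking study supplement. The words about conditions or history cover present as well as past symptoms, and the Visit 3 and Visit 4 sentences remain. The mechanism applies to any exclusion criterion, but this list matters more because its content overlaps with the supplement's effects.

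A reader might infer that the plan orders removal of anyone with a listed reaction. It does not; exclusion is discretionary throughout. A reader might also infer that the reactions would go uncounted or that their follow-up would stop. The recording and follow-up provisions in Sections 10, 13 and 14 do not support that, and Section 15 says reasons for discontinuation will be presented.

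**Conclusion.** The point holds as an ambiguity with a real consequence: as written, the plan permits, but does not require, exclusion of a randomised participant for a local reaction on supplement. Such removal could differ by arm, lose the 12-week endpoint and leave the carnosine arm selected for tolerance.

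The size cannot be derived from the documents. The illustrative shift of 0.015 to 0.075 SD rests on assumed rates and on removal of every reactor, which a discretionary rule would not produce; Section 16 reports no complications in similar earlier trials, so a difference near zero is also possible. It would be wrong to read the illustration as an estimate of bias, or to treat all eight reactions as expected carnosine effects, since Section 16 does not name tiredness. The case for change is that the analysis population should not depend on a judgement about a side effect, and that this can be prevented cheaply.

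**What to change.** State in Section 9 that the Special Conditions are applied as exclusions only before randomisation. State in Sections 9, 10 and 15 that a randomised participant who reports a listed reaction has it recorded as an adverse event, keeps Visits 3 and 4 and the safety check where consent allows, and stays in the intent-to-treat analysis whether or not supplement continues. Distinguish stopping the supplement from leaving the study.

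Ask the sponsor to reconcile item 1 with items 2 and 3 of the same list, and the list with the Discontinued and Medical or Health Concerns text in Section 9, the visit and safety text in Section 10, and the rules on cancelling supplement and holding the trial in Section 14. Which reactions bar entry, and when supplement is stopped or restarted, are clinical decisions for the sponsor.

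The cost is protocol wording only. It adds no visit, measurement or participant to the existing schedule.
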